Sample collection: Participants will be asked to fast for 10-12 hours beginning at 9:00 PM the day prior to each study visit, excluding water, in an attempt to standardize gastrointestinal transit time and minimize delayed absorption of the study intervention due to the presence of food. A study clinician or CTRC nursing staff member will place a peripheral intravenous catheter in the participant’s arm or hand to allow for serial plasma specimen collection. Prior to administration of the *Centella asiatica* product, a baseline plasma sample of one tablespoon (15 mL) will be collected through the catheter using a syringe and transferred immediately into a heparinized Vacutainer tube. The participant will be asked to consume by mouth one of the two doses of *Centella asiatica* product dissolved in 8-12 ounces of warm water, on an empty stomach in the presence of study personnel to ensure compliance. Participants will be asked not to consume food for two hours following consumption of the study intervention to allow for transition into the small intestine and absorption. If signs of hypoglycemia present, participants will be allowed to consume a high glycemic food and monitored for improvement. Serial blood samples (two

Study Title: A pharmacokinetic study of *Centella asiatica* in the elderly

Principal Investigator: [name]

IRB#: 17697

Date: Feb 28 2024

Protocol v4.0

teaspoons (10 mL)/sample) will be obtained through the peripheral intravenous catheter using a syringe over a 12-hour post-administration period (15, 30, 45, 60, 90, 120, 180, 240, 360, 480, 600, and 720 min) (Table 2). Participants will collect their urine for the duration of the study visit (12-hours) to assess for excretion of *Centella asiatica* metabolites.

Tolerability and safety: We will record weight, height, body mass index, age, blood pressure, temperature and pulse rate at each study visit to monitor for adverse events and asymptomatic illnesses that may impact study results (Figure 3, Table 2). Participants will have an electrocardiogram (EKG) at the beginning of each study visit and six hours after intervention administration. Participants will be interviewed and administered a standardized multi-system adverse events questionnaire at the beginning and end of each study visit. This questionnaire has been adapted from the National University of Natural Medicine approved questionnaire and has been included in this IRB submission for approval.

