I.5. Visit 1 and 2 tolerability phone assessment

Participants will be telephoned the day following each study visit to assess for delayed adverse events and/or complications from the intravenous catheter placement using interviews and a standardized multi-system adverse events questionnaire (Figure 3, Table 2). Participants will be instructed to contact a study clinician if they experience any reactions following the phone assessment, and prior to their second study visit or one-week exit interview.

I.6. Exit interview tolerability assessment

Participants will be telephoned one week following the completion of their second study visit, or first study visit if they elect to drop out of the study, to assess for delayed adverse events and/or complications from the intravenous catheter placement using interviews and a standardized multi-system adverse events questionnaire (Figure 3, Table 2).

Table 2. Schedule of study visits and assessments.

	Screening	Visit 1	Visit 1 + 1 day	Visit 2	Visit 2 + 1 day	Visit 2 + 7 days
Event		Study visit	Phone visit	Study visit	Phone visit	Phone visit
Informed consent	•					
Vitals+	•	•		•		
Health screening, biometric assessment	•	•		•		
Electrocardiogram (EKG)		•		•		
Blood draw (CBC, CMP*) and urinalysis	•					
Low plant diet (starting 48h prior to visit)		•		•		
Single dose of intervention		•		•		
Blood collected at intervals (0-12hr) for bioavailability and antioxidant assessment	•^	•		•		
12-hour urine collection, baseline urinalysis		•		•		
Adverse events (AE) questionnaire		•	•	•	•	•

Study Title: A pharmacokinetic study of *Centella asiatica* in the elderly

Principal Investigator: [name]

IRB#: 17697

Date: Feb 28 2024

Protocol v4.0

Vitals include blood pressure, temperature and pulse rate

* CBC = Complete Blood Count with differential; CMP = Comprehensive Metabolic Panel

[^] Single time point

I.7. Subject participation duration

Including the screening visit, a two to four-week interval between doses, and an exit phone interview for adverse event monitoring, it will take a participant six to eight weeks to complete the study.

J. STUDY DURATION

Recruitment and data collection is expected to begin upon approval from the IRB and FDA and continue for seven months. We estimate a total of four months for final data analysis. Total estimated study duration is eleven months (Table 3).

Table 3. Study timeline.

Activity	Month	1-3	4-6			7-9			10-12		
Finalize product manufacture/quality control											

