completed at the screening visit in order to collect data on any/all pre-existing symptoms and their severity, and will serve as baseline data to determine attribution to the study intervention. The Adverse Event Monitoring Form will be administered in person at the beginning and end of Visits 1 and 2, via telephone the day following Visit 1 and 2, and by telephone one week after Visit 2, to assess for acute and delayed adverse events. Electrocardiograms will be performed just prior to administration of *Centella asiatica* product and six hours after intervention to monitor for adverse events.

Participants will be reminded and encouraged during clinic visits to contact a study clinician if a moderate or serious AE occurs. Participants will be given a telephone number they can call at any time to report potential adverse effects. All severe AEs will immediately be reported to the Independent Monitoring Committee (IMC) and the OHSU IRB by the study principal investigator. Severe AEs (SAEs) are defined as events that are life-threatening or result in hospitalization, permanent disability, cancer, death, or another significant outcome.

N.1. Attribution to intervention

At each administration, items identified on the Adverse Event Monitoring Form will be compared to baseline levels to determine if the symptom was pre-existing. If the symptom was pre-existing at the same or a previously greater severity, the symptom will *not* be considered attributable to the study intervention. If the symptom was pre-existing at lesser severity (or was not previously present), the symptom may be considered attributable to the study intervention. If the intervention is considered attributable, [name] and [name], in consultation with the Principal Investigator, will determine if an alternative clinical explanation exists for the adverse event. If an alternative explanation does not exist, the adverse event *will* be considered attributable to the study intervention. If an alternative explanation does exist, the adverse event *will not* be considered attributable to the study intervention.

N.2. Independent Monitoring Committee (IMC)

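### N.1 labels a post-dose symptom not attributable if it was as bad or worse at screening, even when the same-day pre-dose form shows it absent (minor)

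*Combined protocol and SAP*

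**What the plan says.** Section N gives the AE form two roles. At screening it is "completed at the screening visit in order to collect data on any/all pre-existing symptoms and their severity, and will serve as baseline data" for judging attribution. It is then "administered in person at the beginning and end of Visits 1 and 2", by telephone the day after each visit, and by telephone one week after Visit 2. The stated purpose of these later forms is "to assess for acute and delayed adverse events". I.4 confirms the timing: participants are "administered a standardized multi-system adverse events questionnaire at the beginning and end of each study visit".

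N.1 compares each form with baseline levels and has two branches:

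- "If the symptom was pre-existing at the same or a previously greater severity", the symptom is not considered attributable. No further step follows.
- "If the symptom was pre-existing at lesser severity (or was not previously present), the symptom may be considered attributable to the study intervention". Two named study members, consulting the principal investigator, then "will determine if an alternative clinical explanation exists for the adverse event".

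The schedule does not match section N. I.3 lists the screening assessments and includes no AE form. The "Adverse events (AE) questionnaire" row of Table 2 starts at Visit 1 and has no mark under Screening.

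**The concern.** In a single-dose study the natural question about a symptom at the end of the visit is whether it was there just before the dose. The plan collects that information and gives it no role in N.1. The reference is instead a form from a previous visit, and the branch that depends on it is automatic.

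O.1 anticipates transient nausea, reflux or stomach discomfort, and diarrhea. Such complaints can come and go, and F.2.2.1.1 allows reflux medication, so some participants may report them at screening. Both doses in F.1 are active, so no placebo period gives a background rate against which to check the labels. C.4.4 states that no human safety data exist for concentrated water extracts at these doses.

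At stake is which events are called related. The one decision in the plan that uses that label is the stopping rule in H.4, which ends the study if two participants terminate because of intervention-related AEs.

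**Working it through.** The plan gives no figure to reproduce. The check sets the sections side by side and counts forms and intervals.

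**Which form is the baseline?** N.1 does not name one. The paragraph of section N just before it names the screening form and states that its purpose is attribution. No text gives the start-of-visit form that role.

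**What the rule does.** Assume a post-dose symptom no worse than it was wherever it was present before:

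| Screening | Same-day pre-dose | After dose | N.1 as written | Pre-dose form as baseline |
|---|---|---|---|---|
| present | absent | present | not attributable, no review | clinician review |
| present | present | present | not attributable | not attributable |
| absent | present | present | clinician review | not attributable* |
| absent | absent | present | clinician review | clinician review |

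*Unless it first appeared between the two doses; see the fix.

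The first row is the problem. The third row is the opposite error and is less serious, because review can remove the event, although N.1 does not point reviewers to the pre-dose form. A symptom that is worse than at screening goes to review under N.1 whatever the pre-dose form shows.

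**How many forms are involved?** F.2.1 plans 8 participants. Each has 7 scheduled forms after screening: start and end of Visit 1, next day, start and end of Visit 2, next day, and exit call.

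- All forms: 8 × 7 = 56.
- Start-of-visit, pre-dose: 8 × 2 = 16. None is named as a comparator. The one at Visit 2 also serves as follow-up for dose 1.
- Other post-dose: 8 × 5 = 40.

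**How old is the reference?** I.4 puts Visit 1 at least 72 hours (3 days) after screening, with no maximum, and Visit 2 about 2 to 4 weeks after Visit 1. The shortest ages in days are:

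| Form | Screening baseline | Same-visit pre-dose baseline |
|---|---|---|
| End of Visit 1 | 3 | 0 |
| Visit 1 + 1 day | 3 + 1 = 4 | 1 |
| End of Visit 2 | 3 + 14 = 17 | 0 |
| Visit 2 + 1 day | 17 + 1 = 18 | 1 |
| Visit 2 + 7 days | 17 + 7 = 24 | 7 |

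With a 4-week interval, and Visit 1 still at its minimum, the screening form is 3 + 28 = 31 days old at Visit 2.

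**If no screening form is done.** If Table 2 is followed literally, N.1 has no defined baseline. Should staff fall back on the first available form, that is the Visit 1 pre-dose form. The problem then disappears for dose 1 but remains for dose 2, where the reference is at least about 14 days old.

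**How many events are mislabelled?** This needs the joint frequency of a symptom present at screening, absent before dosing and back after dosing at no greater severity. The documents give none of these rates, so no number can be offered.

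**The case against.** The case for leaving the rule alone has several parts.

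- *The operative baseline is unclear.* Usage is mixed. I.4's diet check contrasts screening with baseline at each study visit, and H.1 has the product taken after baseline measurements, but I.2 also speaks of baseline measurements at screening. This stands in part: the contradiction between N and the schedule is itself a finding. It does not rescue N.1, because section N expressly ties attribution to the screening form.
- *The pre-dose form has its own bias.* It is completed after a 10-12 hour fast and 48 hours of restricted diet, before a day with three meals. Habitual reflux may be absent then and return with food. This is a fair point, and it is why screening symptoms should stay available to the clinicians as history. It does not justify automatic exclusion.
- *The form was not available to check.* Its recall window is not shown. If it covers preceding days, the pre-dose form might also record the symptom and fewer events would be affected. This stands.
- *Other eyes see the events.* The investigators review AE forms weekly, participants are interviewed, and the monitoring committee sees un-blinded AE data by organ system. This stands: what is skipped is the alternative-explanation step of N.1.

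A reader might also infer three stronger things that the documents do not support. The first is that every symptom present at screening is excluded; the exclusion requires the same or greater severity at baseline. The second is that a symptom starting after dose 1 and persisting past dose 2 is misattributed. N.1 attributes to the intervention, not to a particular dose, so calling it attributable is correct. The third is that related-AE rates by dose would be distorted; L.1 defines no such summary.

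**Conclusion.** The point holds in a limited form and is minor. As written, N.1 can label a recurrent post-dose symptom unrelated by reference to a form at least 3 days old at Visit 1, or about 17 days at Visit 2, while a same-day form showing it absent goes unused. Section N also relies on a screening form that I.3 and Table 2 do not schedule.

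The effect is on the relatedness label. It would be tempting to say that the stopping rule is compromised, but that is a rare route: a participant would have to leave over a symptom no worse than at screening, mainly after dose 1, when a dose is still to come. H.4 also sends severe events straight to the investigators and the monitoring committee, who judge relatedness themselves. Event detection, severe-AE reporting and the Aim 2 hypothesis of no severe events do not depend on N.1.

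The conclusion assumes that baseline in N.1 means the form section N names, and that the pre-dose form records symptoms present at that time.

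**What to change.** Amend N.1 so that:

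- the baseline for each dose is the AE form completed at the start of that visit, before dosing, recording symptoms present at that time;
- symptoms that first appear between the two doses are judged against the Visit 1 pre-dose form, so that a delayed effect of dose 1 is not absorbed into the Visit 2 baseline;
- any screening form is kept as history for the clinicians' alternative-explanation review and no longer excludes a symptom automatically.

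Make section N, I.3 and Table 2 agree on whether a screening form is done. If participants have already been dosed, the labels can be redone from the case report forms retained under L.3, with reviewers blinded to dose order.

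The cost is a wording amendment with IRB approval and a little more clinician time on recurring background symptoms. No new data are needed, because the pre-dose forms are already scheduled.

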Principal Investigator: [name]

IRB#: 17697

Date: Feb 28 2024

Protocol v4.0

Adverse event (AE)/experience:

- 1) Worsening of pre-existing disease
- 2) Intercurrent illness
- 3) Death
- 4) Major/clinically significant alteration in laboratory values or biometric assessments after beginning product
- 5) Other AE
- 6) Other reasons concerning the participant's health or well-being

The study will be terminated if two participants terminate due to intervention-related adverse events. Severe adverse events will be reviewed immediately by the Principal Investigator, clinical investigators and the Independent Monitoring Committee (IMC) to determine if severity and relatedness warrant termination of the study (Section N).

I. SCREENING AND STUDY ACTIVITIES

I.1. Phone screening

Potential participants will be screened over the phone by a member of the study team, primarily the study coordinator, prior to coming in for the in-person screening visit. A standardized telephone script will be used and has been submitted for IRB approval. The telephone screening will take approximately 10-15 minutes. Potential participants that meet eligibility criteria (Section F.2.2) over the phone will be scheduled for a screening visit.

I.2. Consent process

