Low phytochemical “plant” diet: Due to the nature of the bioactive compounds from *Centella asiatica*, participants will be required to adhere to a “low plant diet” designed by the Oregon Clinical and Translational Research Institute Bionutrition Department at OHSU. They will comply with this diet for 48 hours prior to each study visit, for which they will be given a handout at the screening visit. The diet is essentially limiting intake of fruits, vegetables, coffee, whole grains, chocolate and tea, which may contain compounds similar to those found in *Centella asiatica*. Participants will be provided with food conforming to this diet for the duration of each study visit including three full meals and snacks as needed. To assess for success of the diet, a small amount of the blood obtained at the screening visit will be analyzed for the presence of the bioactive compounds while the participant is following their normal diet and then compared to baseline levels at each study visit. To monitor for dietary compliance, a 48-hour diet diary will be provided to each participant to be filled out each day and brought to each study visit. The diary will also include areas for documenting supplement and medication usage. This has been submitted with this protocol for approval.

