Venipuncture: The potential risks to participants are minimal and reversible. Likely risks include pain and bruising from the intravenous catheter or venipuncture needle insertion. Occasional risks include feeling lightheaded or faint during or immediately after a blood sample is collected. Unlikely risks include swelling, infection, transient hematomas, transient thrombophlebitis, a fractured catheter embolus, or an allergic reaction to the adhesives or sterilization materials used at the venous access point. To minimize risk, catheter insertions and blood draws will be conducted in a seated position and using aseptic technique by trained personnel.

Centella asiatica product: *Centella asiatica* is an edible plant. The Botanical Safety Handbook⁴⁹ classifies *Centella asiatica* as a Class 1 herb, i.e. one that can safely be consumed when used appropriately. The widespread use of *Centella* as a dietary supplement and human studies performed with *Centella asiatica* (Appa Rao, Srinivasan et al. 1973, Tiwari, Singh et al. 2008, Dev, Mohamed et al. 2009, Wattanathorn, Mator et al. 2008, Roushan, Tiwari et al. 2013)¹² support its safety. At the doses given in this study, the risks are expected to be minimal and unlikely. The lowest dosage is based upon allometric scaling from mouse studies in which no toxicity was observed; however, the present product is a concentrated extract, and it is important to establish its safety, particularly in a vulnerable elderly population. We do not anticipate a great increase in adverse effects with the higher dosage, but are aware that they may occur. In particular, we anticipate potential transient gastrointestinal side effects such as nausea, gastric reflux/discomfort or diarrhea. Due to unknown interactions with pharmaceutical medications, we will exclude those on blood thinning medications (e.g. warfarin). See section C.4 above for further information.

Treatment-emergent suicidal ideation and behavior have been identified as a concern for a number of drugs and drug classes. Because of these concerns, a prospective assessment for suicidal ideation and behavior will be monitored. Heisel et al. (2011)¹⁰⁶ have identified a “suicide ideation” subscale in the Geriatric Depression Scale (GDS). We are using the GDS as part of study procedures, and will pay special attention to the identified subscale questions to assess potential risk of suicidal ideation or behaviors.

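### N.1 makes an adverse event unrelated once any alternative clinical explanation is accepted, with no intermediate class, so related events may be undercounted for the H.4 stopping rule and for any tolerability summary based on attribution

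*Combined protocol and SAP*

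**What the plan says.** Section N.1 works in two steps. A symptom already present is removed first: "If the symptom was pre-existing at the same or a previously greater severity, the symptom will *not* be considered attributable to the study intervention". For a symptom that is new or worse, two named assessors, consulting the Principal Investigator, "will determine if an alternative clinical explanation exists for the adverse event". If they find none, the event is attributable. If they find one, the result is fixed: "If an alternative explanation does exist, the adverse event *will not* be considered attributable to the study intervention". The documents contain no other attribution procedure.

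Section H.4 depends on the outcome: "The study will be terminated if two participants terminate due to intervention-related adverse events". It also makes relatedness one of the considerations when a severe event is reviewed for possible termination of the study.

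The conditions at each visit are in I.4. On fasting: "Participants will be asked to fast for 10-12 hours beginning at 9:00 PM the day prior to each study visit", with a further two hours without food after dosing. On the 48-hour diet: "The diet is essentially limiting intake of fruits, vegetables, coffee, whole grains, chocolate and tea". Blood is drawn through a catheter before dosing and at 12 times afterwards. Of the product, O.1 says: "we anticipate potential transient gastrointestinal side effects such as nausea, gastric reflux/discomfort or diarrhea". Of the blood draws it says: "Occasional risks include feeling lightheaded or faint during or immediately after a blood sample is collected".

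**The concern.** The deciding test in N.1 is whether an alternative exists, not whether it is more probable than the product. An event with two credible causes must go into one of two boxes, and the rule sends it to the unrelated one. In this design such events may well arise, because the fast, the diet and the sampling apply to every participant at both visits. Both periods are active (2 g and 4 g), so no placebo rate is available to show how much of the symptom burden the procedures cause.

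Two uses are exposed. The H.4 rule needs only two terminations, so losing even one to the unrelated class can decide whether it is met. Any account of tolerability built on attributable events would also look better than it should. Section C.4.4 says there are no human safety data for concentrated water extracts at these doses, and O.2 says the tolerability data will be carried into trials in patients with cognitive decline or Alzheimer's disease.

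**Working it through.** The plan gives no adverse-event rate, no accuracy for the attribution step and no operating characteristics for the stopping rule. There is therefore no stated figure to reproduce. The check is a reading of the rule against the visit conditions, followed by an illustration.

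**1. Direction for a truly related event.** Suppose the product caused the symptom and it has passed the pre-existing-symptom step. If no alternative is accepted, it is counted; if one is accepted, it is not. For such events the final step can only leave the related count unchanged or lower it.

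**2. Which alternatives the documents supply.**

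| Visit condition (both visits, every participant) | Symptom the documents connect with it |
|---|---|
| 10–12 h fast plus 2 h after dosing, i.e. 12–14 h without food apart from the dosing drink | Possible signs of hypoglycemia (I.4) |
| 48 h low plant diet | None stated |
| 1 baseline + 12 later = 13 blood samples | Light-headedness or faintness, pain, bruising (O.1) |

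Faintness around a blood draw and signs of hypoglycemia therefore have a documented procedural cause. The documents do not link the gastrointestinal effects anticipated for the product to the fast or the diet. That link is plausible, but it is an inference.

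**3. Baseline.** Section N takes the form completed at screening as the baseline for attribution, so it predates the fast and the diet. The same form is given at the beginning of Visits 1 and 2, after both have started, but N.1 does not say how that pre-dose form is used. Table 2 shows no adverse-event questionnaire at screening, so it must be reconciled with Section N.

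**4. Sensitivity of the H.4 rule (illustration).** Let p be the true probability that a participant terminates because of a product-related event, and s the share of such events still called related under N.1. Neither is in the documents, so both are assumed. With 8 independent participants and q = p × s,

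P(at least 2) = 1 − (1 − q)^8 − 8q(1 − q)^7.

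For p = 0.20:
- s = 1.00: q = 0.20, and 1 − 0.168 − 0.336 = 0.497 (from unrounded terms).
- s = 0.50: q = 0.10, and 1 − 0.430 − 0.383 = 0.187.

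| p | s = 1.00 | s = 0.75 | s = 0.50 | s = 0.25 |
|---|---|---|---|---|
| 0.05 | 0.057 | 0.034 | 0.016 | 0.004 |
| 0.10 | 0.187 | 0.116 | 0.057 | 0.016 |
| 0.20 | 0.497 | 0.343 | 0.187 | 0.057 |
| 0.30 | 0.745 | 0.568 | 0.343 | 0.116 |
| 0.50 | 0.965 | 0.865 | 0.633 | 0.264 |

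With 6 participants (the 25% dropout case in F.2.1) and p = 0.30, the row is 0.580, 0.406, 0.224, 0.069. The s = 1.00 column is the case in which no truly related event is ruled out. The table shows direction and possible size, not an estimate for this trial.

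**The case against.** Several points on the other side stand.

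- **Clinical judgement.** N.1 asks for a clinical explanation, accepted by named assessors. They could decline to accept a procedure common to every visit. So the documents support that events may be undercounted, not that they are. The wording still does not require assessors to weigh likelihood, and the classification should not rest on their reading it generously.
- **Both directions.** When no alternative is found, the event is attributable by default, also without weighing. A coincidental new item on the 91-point form, or a symptom of the fast or diet measured against a screening baseline, could then be called related. A reader might infer that the error runs only toward good tolerability. That is true of the final step for truly related events, but the net direction over all events is not established.
- **Aim 2.** The endpoint in A.3 and the hypothesis in Section B concern tolerability, acute events and severe events, with no restriction to attributable ones. L.1 also plans within-subject comparison of outcomes between doses. Aim 2 is affected only if tolerability is summarised by attribution. However, L.1 specifies no adverse-event table, so nothing rules that out.
- **Safeguards.** All severe events go to the monitoring committee and the IRB whatever their attribution. The committee sees unblinded events by organ system, with no stated limit to attributable ones. H.4 allows withdrawal for an adverse event without a finding of relatedness. These are real but partial: the anticipated effects are transient and not described as severe, and the committee meets twice a year against seven months of recruitment and data collection.
- **Narrow reach.** H.4 counts only participants who terminate, and nothing in the documents suggests the anticipated transient effects would lead to that.

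**Conclusion.** The concern holds in a limited form. N.1 is an all-or-nothing rule with no likelihood test and no intermediate class, and it is the only attribution procedure behind the H.4 count. Combined with universal fasting, diet and sampling and no placebo period, it may undercount related events for H.4 and for any tolerability summary based on attribution.

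The size cannot be computed from the documents. The illustration (0.497 to 0.187 at p = 0.20, and 0.745 to 0.343 at p = 0.30, when half of the related terminations are ruled out) rests on assumed p and s and on independent participants.

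A reader might go further and infer that the related count for the anticipated effects could be zero whatever the true rate. The documents do not support this. No section names the fast or diet as a cause of nausea, reflux or diarrhea, and the effects listed for blood draws are not gastrointestinal. Nor can faintness be treated as an established product effect: the blood-pressure decreases in C.4.1 were seen in studies of six months' intake and described as mild, with no faintness reported.

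**What to change.** - **Grade relatedness.** Replace the last two sentences of N.1 with a scale such as not related, possibly related and probably related. Use not related only when the alternative is judged more likely than the product, and record the reason. Procedure-specific events, such as catheter bruising, may still be classed as not related.
- **Use the pre-dose form.** State in N.1 that the form given at the start of each visit separates symptoms present before dosing from those arising after it. Reconcile Section N with Table 2 on whether the form is completed at screening.
- **Report all events.** For Aim 2, tabulate all treatment-emergent adverse events by dose, within participant, regardless of attribution.
- **Reconcile N.1 with H.4.** The sponsor should state which relatedness classes the H.4 rule counts. That choice is the sponsor's and is not proposed here.

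The cost is revised wording and one table, with no new data collection. The downside is that more events will be classed as possibly related and tolerability will look slightly less favourable. Depending on the classes the sponsor chooses, the H.4 rule could also be met somewhat more easily, including on events that the procedures caused.
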